6.3.1 Pharmacokinetic Evaluation

Plasma samples will be collected from all subjects and analysed to determine levels of lubiprostone (if measurable) and metabolite M3. These concentration-time data will be used in a population PK analysis. PK samples will be taken under non-fasting conditions. The samples will be collected via direct venepuncture. Approximately 8 mL of blood will be taken for each sample such that the total of all PK samples does not exceed 50 mL or 5 mL/kg of body weight.

7. ADVERSE AND SERIOUS ADVERSE EVENTS

As defined in ICH GCP Guideline E6,¹⁴ an AE is any untoward medical occurrence in a clinical investigation subject administered a pharmaceutical product and which does not necessarily have a causal relationship with this treatment. An AE can therefore be any unfavorable and unintended sign (including an abnormal laboratory finding), symptom, disease or exacerbation of a pre-existing condition temporally associated with the use of a medicinal (investigation) product, whether or not related to the medicinal product. For this study, all safety information will be collected from the time of informed consent and any untoward medical occurrence after enrolment will be defined as an AE. Adverse events that are reported after initiation of study medication will be defined as treatment-emergent AEs.

In this study, faecal impaction and bone fractures will be captured as AEs. The events of faecal impaction will be used for the analysis of the faecal impaction frequency during the study (see [Section 8.6.2.5](#)).

Each AE requires a complete and thorough description including date of onset, duration, intensity/severity, its relationship to the study drug and any corrective actions taken. Each AE should also be categorized as “serious” or “non-serious”.

Timely, accurate, and complete reporting and analysis of safety information from the clinical study are crucial for the protection of subjects and are mandated by regulatory agencies worldwide.

7.1 Definitions and Descriptions

7.1.1 Serious Adverse Event

A serious adverse event (SAE) is any untoward medical occurrence that, at any dose:

- Results in death;
- Is life-threatening (the subject was at risk of death at the time of the event. It does not refer to an event which hypothetically might have caused death if it were more severe);
- Requires hospitalization or prolongation of existing hospitalization;
 - This criterion applies if the event requires inpatient hospitalization and results in an overnight stay in hospital or, if in the opinion of the investigator, prolongs an existing hospitalization.
 - Hospitalizations for less than 24 hours with no admission are not considered “hospitalization”.
 - A hospitalization (including hospitalization for an elective procedure or routinely scheduled treatment or pre-planned procedures) for a pre-existing condition which has not worsened does not constitute an SAE.
- Results in persistent or significant disability/incapacity;
- Is a congenital anomaly/birth defect; and/or
- Is an important medical event (an event that may not fit the other criteria for a SAE as listed above, but based upon appropriate medical judgment, may jeopardize the subject or may require intervention to prevent one of the outcomes listed above). Examples of such events (per 21 CFR 312.32¹⁵) are intensive treatment in an emergency room or at home for allergic bronchospasm, blood dyscrasias or convulsions that do not result in hospitalization or development of drug dependency or drug abuse.

7.1.2 Non-serious Adverse Event

A non-serious AE is any event that does not meet the above-mentioned SAE definition.

7.1.3 Severity

The severity of each AE will be determined based upon the following criteria:

- Mild:** Transient symptoms, no interference with subject's daily activities. Less than 48 hours, no medical intervention/therapy required.
- Moderate:** Marked symptoms, moderate interference with the subject's daily activities. No or minimal medical intervention/therapy required.
- Severe:** Considerable interference with the subject's daily activities. Medical intervention/therapy required; hospitalization possible.

7.1.4 Relationship to Study Medication

The relationship to study medication will be determined and recorded on eCRF by an Investigator using the following criteria based on the World Health Organization (WHO) classification:

Causality	Definition
Unrelated	Concurrent illness, concurrent medication, or other known cause is clearly responsible for the adverse event OR based upon available information regarding subject history, disease process, relationship of adverse event to dosing, and drug pharmacology, a relationship between the drug and adverse event is unlikely.
Possible	The adverse event follows a reasonable sequence from the time of drug administration, but could also have been produced by the subject's clinical state or by other drugs administered to the subject. Event with a time to drug intake that makes a relationship improbable (but not impossible). Disease or other drugs provide plausible explanations
Probably	The adverse event follows a reasonable sequence from the time of drug administration, follows a known response pattern of the study treatment class, is confirmed by improvement on stopping the study treatment is the most likely of all causes. Event with reasonable time relationship to drug intake: 
• Unlikely to be attributed to disease or other drugs• Response to withdrawal clinically reasonable• Rechallenge not required
Definite	The adverse event follows a reasonable sequence from the time of drug administration, follows a known response pattern of the study treatment class, is confirmed by improvement on stopping the study treatment, and there is no other reasonable cause exists.

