6.3 Safety Evaluations

The following safety evaluations will be performed during the study to measure the safety of the study medication:

Adverse Events: AEs will be reported by the subject from the time of informed consent through the end of the follow-up period. AEs will be followed by the Investigator as determined by Sponsor or designee. Further details on AE reporting are provided in [Section 7](#). Any study medication related AEs persisting at the end of the study will be followed until resolution, or until a clinically stable endpoint has been reached.

In this study, faecal impaction and bone fractures will be captured as AEs. The events of faecal impaction will be used for the analysis of the fecal impaction frequency during the study (see [Section 8.6.2.5](#)).

Clinical Laboratory Tests: The following laboratory tests will be conducted and the appropriate Investigator shall determine the clinical significance of any out-of-range values.

- **Hematology Panel:** Hemoglobin, hematocrit, MCV, MCH, MCHC, RBC, WBC, white blood cell with absolute counts and percent differentials (neutrophils, lymphocytes, monocytes, eosinophils, basophils), platelet count.
- **Chemistry Panel:** Total cholesterol, triglycerides, glucose, total protein, albumin, alkaline phosphatase, AST, ALT, GGT, iron, LDH, total bilirubin, direct bilirubin, BUN, uric acid, creatinine, sodium, potassium, chloride, bicarbonate, calcium, phosphorus, magnesium.
- **Urinalysis:** Protein, glucose, ketones, occult blood, pH, specific gravity, color, appearance, leukocyte esterase, nitrite, bilirubin, and macroscopic examination. Microscopic examination will be done if abnormalities are present. Urine samples will be collected, when possible.

Physical Examination: Physical examinations will be conducted at various timepoints during the study. Any new post treatment findings or changes, as noted by the Investigator, will be reported as an AE.

Vital Signs:

Vital signs (including height and weight at designated visits) will be recorded during the study. Any post treatment clinically significant changes in vital signs (including weight) shall be noted by the Investigator and reported as an AE. Additional guidance regarding assessment of changes in blood pressure and heart rate are provided below.

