7.2 Recording and Reporting of Adverse Events

All AEs will be recorded in the source document and applicable eCRF(s) from the time the informed consent is signed until the end of study. AEs occurring prior to the first dose of study drug will be considered non-treatment emergent. Any ongoing AEs will be followed until they are resolved, stabilized, or until 30 days after the end of treatment exposure. The Investigator shall notify the Sponsor at any time when an SAE is believed to be related to the administration of study medication, even after the end of the study. At any time during the study, those events meeting the definition of an Immediately Reportable Event (IRE) must be recorded on source document, IRE Reporting Form, and applicable eCRF(s), and then reported to Sponsor or designee using the IRE Reporting Form as specified in [Section 7.2.1](#).

All AEs that have not resolved by the end of the study, or that have not resolved upon discontinuation of the subject's participation in the study, must be followed until either:

- the event resolves;
- the event stabilizes;
- the event returns to baseline, if a baseline value is available;
- the event can be attributed to other than the study medication, or to other than study conduct;
- the Investigator does not anticipate any further improvement or worsening of the event.

All AEs, regardless of seriousness, severity or presumed relationship to study medication, must be recorded using medical terminology in the source document and in the eCRF. Whenever possible, diagnoses should be given when signs and symptoms are due to a common etiology (e.g., cough, runny nose, sneezing, sore throat, and head congestion should be reported as "upper respiratory infection"). Investigators must record on the source document and eCRF their opinion concerning the relationship of the AE to study therapy and the severity of the event. All measures required for AE management must be recorded in the source document and reported according to Sponsor instructions.

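### The causality scale in section 7.1.4 allows an event with an improbable link to the drug to be coded either Unrelated or Possible, with no tie-break

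*Combined protocol and SAP*

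**What the plan says.** Section 7.1.4 makes causality an investigator judgement: "The relationship to study medication will be determined and recorded on eCRF by an Investigator". It defines four levels (*Unrelated*, *Possible*, *Probably* and *Definite*) and has no separate level for an unlikely relationship.

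- *Unrelated* has two limbs. The first is a clearly responsible other cause. The second is a judgement, drawing on factors that include "relationship of adverse event to dosing, and drug pharmacology", that "a relationship between the drug and adverse event is unlikely".
- *Possible* opens with "The adverse event follows a reasonable sequence from the time of drug administration, but could also have been produced by the subject's clinical state"; concomitant drugs are named as another source. It then adds "Event with a time to drug intake that makes a relationship improbable (but not impossible", and closes by saying that disease or other drugs offer plausible explanations.

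The classification is used in three places:

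- Section 8.5.2 plans AE summaries by causality.
- Section 6.3 says: "Any study medication related AEs persisting at the end of the study will be followed until resolution", or until a clinically stable endpoint.
- Section 7.2 says: "The Investigator shall notify the Sponsor at any time when an SAE is believed to be related to the administration of study medication", including after the study has ended.

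**The concern.** A causality scale is useful only if each event has one home. Here the idea of an unlikely relationship appears in two levels, and these lie on either side of the most natural dividing line between related and not related. Two sites could read the definitions correctly and still code the same event differently.

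This matters more here than in a controlled trial. Safety is the primary objective (section 2.1). There is no randomisation and every subject receives lubiprostone (section 5.5.2), so no concurrent untreated group shows the background rate of events. Readers of the report will give weight to the investigators' attributions. With about 130 sites planned (section 3), differing readings of an ambiguous definition are likely. They would add between-site variation that has nothing to do with the drug.

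**Working it through.** The plan states no figure on this point and no arithmetic applies. The check is a comparison of the definitions and of the places where they are used.

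**1. Do the two levels overlap?** The second limb of *Unrelated* asks whether a link is unlikely, and names the relation to dosing as one ground. The second sentence of *Possible* describes timing that makes a link improbable without excluding it. In ordinary use, unlikely and improbable-but-not-impossible mean the same, and both tests look at timing relative to dosing. They overlap.

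**2. Which events fall in the overlap?** If another cause is clearly responsible, the first limb of *Unrelated* settles the matter. The overlap concerns an event whose timing makes a link improbable and for which other explanations are plausible but none is clearly responsible. That event meets the second limb of *Unrelated* and also the second and third sentences of *Possible*.

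**3. Is *Possible* consistent with itself?** Its first sentence reads "The adverse event follows a reasonable sequence from the time of drug administration, but could also have been produced by" other factors. Its second sentence admits timing that makes a link improbable. An investigator cannot tell whether reasonable timing is required for this level.

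**4. Is there a tie-break?** Section 7.1.4 gives none. Sections 6.3, 7.2 and 8.5.2 use causality or relatedness without defining it further. None of them says which levels count as related.

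**5. What depends on the answer?**

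- *Directly:* the summaries by causality in 8.5.2.
- *At the margin:* follow-up of related AEs under 6.3, because 7.2 already requires unresolved AEs to be followed whatever their relationship; and notification of related serious AEs after the end of the study under 7.2.
- *Not at all:* the AE endpoint in 2.2.1, which is incidence by system organ class and preferred term; the Fisher or chi-square comparisons in 8.5.2 at system organ class and any-event level; the recording of all AEs under 7.2; and the 24-hour reporting of all serious AEs under 7.2.1.

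**6. How large is the effect?** It depends on the number of subjects whose only AEs lie in the overlap, and on how sites divide in coding them. The documents give neither.

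**The case against.** The strongest reply is that this is one loosely worded sentence affecting a secondary summary. The safety endpoint is all-cause, the group comparisons do not use causality, and laboratory, vital-sign and bone-density data and the safety board's review do not depend on it. All of that stands, and it limits the point.

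A second reply is that the detail may sit elsewhere. Section 8 defers to a statistical analysis plan and section 7.2.1 refers to a safety reporting plan. Either might define which levels count as related or give coding guidance, but the combined document does not include such text. This could make part of the fix redundant. It would not remove the conflict inside 7.1.4, which is the text that investigators are told to apply.

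A reader might infer more than the documents support:

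- *That an ordinary intercurrent illness, such as a cold, would be coded either way.* It would not. A clearly responsible concurrent illness is *Unrelated* under the first limb.
- *That safety reporting as a whole turns on relatedness.* It does not. Sections 7.2 and 7.2.1 require all AEs to be recorded, and all serious AEs to be reported within 24 hours, whatever their relationship.
- *That the wording on improvement after stopping treatment, in the two upper levels, makes the problem worse.* It affects only whether an event reaches *Probably* or *Definite*. It moves nothing across a line between *Unrelated* and *Possible*, and asking for a withdrawal response before assigning the highest certainty is a normal choice.

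**Conclusion.** The overlap is real and can be read directly from 7.1.4. It is a contradiction between stated definitions rather than a missing detail. The planned summaries by causality will carry avoidable between-site variation. There is a smaller effect on the follow-up of related AEs and on the notification of related serious AEs after the study.

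The effect on a split into related and not related rests on one assumption: that the cut falls between *Unrelated* and *Possible*. That is the natural cut on this scale, but the documents neither state it nor name a table of drug-related events. Summaries by individual level are affected wherever the cut falls.

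A reader might infer that the causality results could not be interpreted, or might want a range for the related-event rate. Neither is supported. Without AE rates, any range would come from invented inputs, and its ends would require every site to resolve every ambiguous event in the same direction. The right conclusion is a removable source of noise, of unknown size, in one planned safety summary. The all-cause safety analysis is intact.

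**What to change.** Make the levels mutually exclusive. Remove the improbable-timing sentence from *Possible* in 7.1.4, so that the level rests on a reasonable time sequence with other plausible causes. Then place improbable events in one category only. There are two options:

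- leave them in *Unrelated*, whose text already covers an unlikely relationship; or
- add a separate *Unlikely* level, reported on its own line.

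In either case, state in 8.5.2 which levels count as related. Carry the change into the eCRF completion guidance and a short memo to sites.

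The cost is modest but not nil. Events already coded may need a query, and the scale may then differ from that of the preceding study, which complicates side-by-side reading. Moving improbable events into *Unrelated* also lowers the related-AE count, which is the less cautious direction for a paediatric safety study. A separate *Unlikely* line avoids hiding those events, at the price of one more level for sites to apply.

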7.1.5 Onset and Duration

The date and time the event was reported to investigator will be recorded, as well as the start date and time and resolution date and time of the event.

7.2 Recording and Reporting of Adverse Events

All AEs will be recorded in the source document and applicable eCRF(s) from the time the informed consent is signed until the end of study. AEs occurring prior to the first dose of study drug will be considered non-treatment emergent. Any ongoing AEs will be followed until they are resolved, stabilized, or until 30 days after the end of treatment exposure. The Investigator shall notify the Sponsor at any time when an SAE is believed to be related to the administration of study medication, even after the end of the study. At any time during the study, those events meeting the definition of an Immediately Reportable Event (IRE) must be recorded on source document, IRE Reporting Form, and applicable eCRF(s), and then reported to Sponsor or designee using the IRE Reporting Form as specified in [Section 7.2.1](#).

All AEs that have not resolved by the end of the study, or that have not resolved upon discontinuation of the subject's participation in the study, must be followed until either:

- the event resolves;
- the event stabilizes;
- the event returns to baseline, if a baseline value is available;
- the event can be attributed to other than the study medication, or to other than study conduct;
- the Investigator does not anticipate any further improvement or worsening of the event.

All AEs, regardless of seriousness, severity or presumed relationship to study medication, must be recorded using medical terminology in the source document and in the eCRF. Whenever possible, diagnoses should be given when signs and symptoms are due to a common etiology (e.g., cough, runny nose, sneezing, sore throat, and head congestion should be reported as "upper respiratory infection"). Investigators must record on the source document and eCRF their opinion concerning the relationship of the AE to study therapy and the severity of the event. All measures required for AE management must be recorded in the source document and reported according to Sponsor instructions.

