- Collect PK samples – Pre-dose and 1 sample between 30 and 90 minutes after dose administration (2 samples total). PK samples will be taken under non-fasting conditions. The samples will be collected via direct venepuncture. Approximately 8 mL of blood will be taken for each sample (16 mL in total) such that the total of all PK samples does not exceed 50 mL or 5 mL/kg of body weight;
- Review and record any new AEs and follow-up on any ongoing AEs;
- Update Concomitant Therapy – Concomitant medications (prescribed and over-the-counter [OTC]) used since the last visit will be reviewed. The subject or parent/legal

guardian should again be instructed not to use any prescription or OTC laxatives unless prescribed by the Investigator;

- Review and discuss rescue medication use and remind subject or parent/legal guardian to record rescue medication use in electronic diary;
- The electronic diary dispensed to the subject or parent/legal guardian in the previous blinded study (SAG/0211PFC-1131) will continue to be used. If necessary the subject or parent/legal guardian will receive another demonstration and set of instructions for use. Ensure that the electronic diary is set to capture treatment-related responses associated with this long-term safety study;
- Dispense first bottle of study medication, provide dosing instructions and remind the subject or parent/legal guardian to bring the bottle with any remaining study medication to every visit;
- Observe the subject or parent/legal guardian as he/she administers the first dose of study medication while in the clinic. Over the next 1 hour, monitor subject for any adverse reactions. Ensure blood pressure and heart rate are collected at 1 hour postdose as described above;
- Schedule the next clinic visit (Visit 10/Study Day 8).

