6.1.3 Treatment Period

The treatment period will begin at the Enrolment Visit on the day the first dose of study medication is administered (Study Day 1) and will end upon administration of the last dose.

Note: If at any time during the study, the subject discontinues from the study, the subject should be withdrawn from the study and complete the final visit of the treatment period (Visit 16) and the Follow-up Visit (Visit 17). All subjects who withdraw from the study after Visit 12 (Month 3) should have a final DXA assessment performed. The DXA assessment will only be required for subjects that were originally part of the DXA subgroup.

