8.5.2 Adverse Events

The original terms used in the eCRF by Investigators to identify AEs will be coded to MedDRA® system organ class and preferred terms. Adverse events will be summarized in terms of incidence per dose group and overall. The incidence of an AE is defined as the number of subjects who experienced at least one episode during the study. Adverse event incidence rates will be summarized by system organ class (SOC) and preferred term (as determined by the coding).

Whatever the level of classification, if a subject experiences multiple episodes of an event within the given time reference, then the event is only counted once. Further, for summaries by severity or causality, the most severe event is chosen for a subject if that subject experiences multiple episodes of the same event.

In this study, faecal impaction and bone fractures will be captured as AEs. The events of faecal impaction will be used for the analysis of the faecal impaction frequency during the study (see [Section 8.6.2.6](#)).

AEs with onset dates after administration of the first dose of study medication or prior to the last day of treatment + 7 days will be considered treatment-emergent. Events with completely or partially missing onset dates will be included in the tabulations, unless the available partial date information clearly indicates that the event happened outside of the treatment period.

P-values from Fisher's exact test or chi-square test will be presented in the AE summary tables. The test will be performed to compare incidence rates at the SOC and "At Least One Event" level between the two treatment groups.

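### Three conflicting definitions of a treatment-emergent AE, and no rule for AEs that began on lubiprostone in study 1131 and are ongoing at Visit 9

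*Combined protocol and SAP*

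**What the plan says.** The protocol defines treatment-emergence in three places.

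- Section 7, by report date: "Adverse events that are reported after initiation of study medication will be defined as treatment-emergent AEs".
- Section 7.2, by occurrence relative to the first dose: "AEs occurring prior to the first dose of study drug will be considered non-treatment emergent".
- Section 8.5.2, by onset date with an upper limit, the two parts joined by 'or': "AEs with onset dates after administration of the first dose of study medication or prior to the last day of treatment + 7 days" count as treatment-emergent.

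The reference dose is the first one in this study: Section 6.1.3 dates the treatment period from Visit 9, Study Day 1. Visit 9 coincides with Visit 7 of study 1131 (Section 3.1), and children who were on lubiprostone there stay on the dose they had reached (Sections 1.3, 3 and 5.5.2).

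On counting, Section 8.5.2 says: "The incidence of an AE is defined as the number of subjects who experienced at least one episode during the study". It does not say whether the tables are limited to treatment-emergent events. For collection, Section 6.1.2 tells the site at Visit 9: "Review and record any new AEs and follow-up on any ongoing AEs".

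**The concern.** For a child who took lubiprostone in 1131, Study Day 1 of the extension is not the start of treatment. An AE that began on the drug during the 12 weeks of 1131 and is still present months later has its onset before this study's first dose. Calling it non-treatment-emergent misdescribes it, because the child was on the drug at onset and has continued it. How such an event persists on continued treatment is something a long-term safety study should show, and Section 2.1 makes safety the primary objective.

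The conflict between the definitions also matters in its own right. Section 8.5.2 plans Fisher's exact or chi-square tests between the two dose groups at the SOC and any-event levels. If the set of events entering those tables is not fixed in advance, the incidence figures and the p-values depend on which section the programmer follows.

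**Working it through.** No sample-size, power or alpha figure is involved, so the check applies each rule to a set of test events. The last dose is taken on Day 253 (Visit 16 in the schedule; Section 5.5 places the last dose on that day). The upper limit in Section 8.5.2 is then Day 253 + 7 = Day 260. The onset and report days below are illustrative assumptions. TE means treatment-emergent.

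| Test event | Section 7 (reported after first dose) | Section 7.2 (not before first dose) | Section 8.5.2, literal 'or' | Section 8.5.2 read as 'and' |
|---|---|---|---|---|
| Carried over, onset Day -30, known before dosing | not TE | not TE | TE | not TE |
| Carried over, onset Day -30, first reported Day 8 | TE | not TE | TE | not TE |
| New, onset Day 20 | TE | TE | TE | TE |
| New, onset Day 258 (last dose + 5) | TE | TE | TE | TE |
| Late, onset Day 270 (last dose + 17) | TE | TE | TE | not TE |

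Four things follow.

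1. The literal 'or' defines nothing. Any onset after Day 1 meets the first part and any onset before Day 260 meets the second, so every date qualifies. It also contradicts Section 7.2 for any event before dosing.
2. The workable reading is 'and'. The rationale in the Amendment 3 summary for shortening the excluded-medication period supports it, since it treats 7 days after stopping as a real limit on treatment-emergence.
3. Under 'and', and under Section 7.2, the carried-over event is not treatment-emergent whether it is reported early or late. Under Section 7 the answer turns on when someone mentioned it.
4. Events late in follow-up are also unsettled. From Day 260 to the Week 40 visit on Day 281 is 281 - 260 = 21 days in which 'and' excludes a new event and the other rules include it.

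Whether the incidence tables omit the carried-over event is a matter of inference. Section 8.5.2 sets out treatment-emergence within the AE analysis. It then keeps events with incomplete onset dates in the tables unless what is known of the date places them outside the treatment period. An event with a known onset before Study Day 1 is outside it. Section 7 points the same way, because it defines an AE of this study as something occurring after enrolment.

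**The case against.** The strongest case on the other side has four parts.

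- **Section 8.5.2 as printed includes the event, and nothing there limits the tables to treatment-emergent AEs.** Both statements are correct. The first rests on an 'or' that would admit every event, so it cannot be the intended rule. The second stands, which is why omission is called likely and not certain.
- **The gap is narrow.** This stands. A reader might infer that long-lasting drug AEs in general disappear from the long-term tables. The documents do not support that. An AE starting in the extension and within the treatment period counts under every rule, however long it lasts, and so does any such event in a former placebo child. Section 7 counts exacerbation of a pre-existing condition as an AE, and Section 7.2.4 treats further worsening of an abnormal laboratory value similarly. Exclusion criterion 2 removes children whose 1131 event is clinically significant and would limit participation. What remains is an event with onset in 1131, tolerable at entry and persisting without worsening.
- **The data are collected.** This stands too. Ongoing AEs are reviewed at Visit 9 and later visits, and start and resolution dates are recorded (Section 7.1.5). Collection does not settle tabulation. A reader might also infer that 1131 stops following such events at its Visit 7, but the 1131 protocol is not available and this cannot be asserted.
- **The SAP may deal with it.** Detailed methods are left to a SAP whose text is not in the document reviewed, so a carry-over rule there cannot be ruled out. Section 8.5.2 does not refer this point to the SAP, however, as Section 8.6.1.1 does for missing data.

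**Conclusion.** The point holds in this limited form. Sections 7, 7.2 and 8.5.2 conflict, and Section 8.5.2 as written does not discriminate between events. On Section 7.2, and on the only workable reading of Section 8.5.2, an AE that began on lubiprostone in 1131 and persists without worsening is labelled non-treatment-emergent although the drug is continued. Its absence from the incidence tables is a reasonable inference from the missing-date rule, not a stated rule.

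The size cannot be given. A count would need the 1131 allocation ratio and the share of children entering with an ongoing drug-onset AE, and the documents supply neither. The effect on the any-event row would be smaller than any such count, because a child with another AE during the 36 weeks is already in that row.

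A reader might conclude that treatment-emergence should run from the first 1131 dose in all former lubiprostone children. That does not follow. It would bring in 1131 events that had resolved before rollover. It would also give those children 12 + 36 = 48 weeks at risk against 36 for former placebo children, within the dose groups being tested.

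The conclusion assumes that no carry-over rule exists in the unseen SAP.

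**What to change.** 1. Put one definition in Sections 7, 7.2 and 8.5.2: onset or worsening on or after the first dose in this study, **and** no later than the last treatment day plus 7 days. Remove the report-date wording from Section 7.
2. State in Section 8.5.2 that the AE incidence tables and the tests between dose groups use this definition.
3. Report AEs ongoing at Visit 9 in a separately labelled row or table, split by 1131 treatment (onset on lubiprostone and ongoing at rollover; onset on placebo and ongoing at rollover), with duration and outcome. Link the records through the subject number retained from 1131 (Section 5.5.3), and flag them so that pooled summaries do not count them twice.
4. Leave the main treatment-emergent tables anchored to the first dose in this study.

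The cost is a wording change in three protocol sections and in the SAP, a merge with the 1131 AE data, and one added display. The safety display may look slightly less favourable. No trial procedure changes.
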